13.5.2.2.2 HORIZON INTENSIVE

Binary secondary outcomes will use the same fixed and random effects, and uninformative priors. Instead of a linear mixed model, a logistic mixed model will be used. Other outcomes not falling into these categories will reflect the analysis methods used in the trial.

13.5.3 Statistical methods for exploratory analyses

13.5.3.1 CONNECT

To explore individual differences, a normative modelling framework has been developed by CONNECT researchers for use in multimodal neonatal brain imaging data, that is both sensitive to brain growth and the diffuse brain changes seen following prematurity and in individuals with autism across childhood and adulthood. This approach provides an individual index of variation from the typical distribution from as early as birth, corrected for age or sex, per modality and region, capturing inter-person heterogeneity. This measure of variation has also proven a useful intermediate phenotype to interrogate pathways out to cognitive function in early life. An important advantage of our approach is that we can develop growth curves across different MRI modalities. We will use 'normative modelling' (Gaussian Process Regression or similar Bayesian approach) to assess brain maturation of patients in each study arm with reference to adolescent brain structural, functional and metabolite reference values built from existing studies. An individual Z-score then captures deviations from age-expected reference and can be used to examine either correlations with outcome measures or individual differences in brain changes with respect to GnRHs.

13.6 Adherence

To be defined in the Statistical Analysis Plan.

13.7 Interim analyses (statistical)

Currently, no interim analysis is planned either for futility or for efficacy in either TRIAL or HORIZON INTENSIVE. By using the Bayesian framework for analyses, there is no penalty in the form of type 1 error which is common for frequentist approaches, and as such does not need to be factored in to sample size calculations.

Interim analyses therefore may happen, but only at the recommendation of the DMC and the PSC (or the funder, via the PSC). Only data which the DMC and PSC deem relevant will be analysed at these timepoints. These are the only two committees that may call for an interim analysis of the data. If these committees do not call for interim analyses during TRIAL or HORIZON INTENSIVE, then no interim analyses will be carried out.

The electronic version of this document is the latest version. It is responsibility of the individual to ensure that any paper material is the current version. Printed material is uncontrolled documentation.

If an interim analysis is deemed appropriate, then the results of any such analysis will be shared with the DMC only in the first instance. It is then within the remit of the DMC to determine if it is important for the PSC or PMG should see the results. For example, if a decision is to be made based on the interim analyses, the DMC will make their recommendation to the PSC and depending on the strength of evidence from the data, may determine that the PSC does not need to see the data as there is no ambiguity.

If a decision is to be made, the PSC will advise the sponsor in making the final decision on stopping, continuation, or any potential extension to the funding period.

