13.4 Sample size justification

13.4.1 Trial

The anticipated sample size is approximately 226 participants. This sample size is based on the expected eligible clinic prevalence of gender-related distress, allowing for sufficient power to estimate the posterior distributions of treatment effects and to detect meaningful differences and associations in the primary and secondary outcomes.

Using simulations, it was determined that with 226 participants the trial would have the equivalent of 91% power with a standardised effect size (SES) of 0.525. For the primary outcome, the SES of 0.525 means a difference of 5.25 points on the standardised KIDSCREEN-10 t-score, where the standard deviation is 10 for all t-scores at all timepoints.

If recruitment is lower than expected, the probability of detecting the same SES will be lower. If only 150 participants are recruited, the trial would still have the equivalent of 80% power to detect the SES of 0.525.

As the eligibility criteria for the trial cannot be changed or widened as would be common in a poorly recruiting trial, nor more sites added, other options would have to be considered to reach the target sample size of 226. This could include extending the recruitment period and therefore timeline for the trial. Interim analyses can also be carried out at pre-specified points where decisions on the continuation of the trial can be taken. All amendments to the trial will be approved by both the DMC and the PSC committees before being enacted.

The electronic version of this document is the latest version. It is responsibility of the individual to ensure that any paper material is the current version. Printed material is uncontrolled documentation.

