The analysis of the primary outcome will be carried out using the Bayesian framework. Using the Bayesian framework means that the analysis will have to specify priors and allows for the analysis to give credible intervals, as opposed to confidence intervals, that are much easier to interpret.

The primary analysis model will be a Bayesian linear mixed model. The baseline score for the primary outcome will be included as a fixed effect, alongside the stratifying factors of site, birth registered sex, tanner stage and diagnosis of a neurodevelopmental disorder or trait. Random effects for participant will be included to account for clustering of longitudinal data within participants.

As this will be carried out using the Bayesian framework, priors used for all parameters estimated will be uninformative, flat priors. Derivation of the single primary outcome is detailed fully in the PATHWAYS TRIAL Statistical Analysis Plan.

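### Section 13.7 is wrong that Bayesian interim looks carry no type 1 error cost: with flat priors, an efficacy look at an unchanged threshold inflates false positives as an uncorrected frequentist look would

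*Protocol*

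**What the plan says.** Section 13.7 begins: "Currently, no interim analysis is planned either for futility or for efficacy in either TRIAL or HORIZON INTENSIVE". It then says that with Bayesian analysis "there is no penalty in the form of type 1 error which is common for frequentist approaches", and that it "as such does not need to be factored in to sample size calculations". From this it infers that looks may take place if the DMC and the PSC (or the funder acting through the PSC) recommend them. The section fixes no number, timing or threshold. On what may follow from a look, "the PSC will advise the sponsor in making the final decision on stopping, continuation, or any potential extension to the funding period".

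Three other places bear on this:

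- Section 13.5.1.1, on the primary model: "priors used for all parameters estimated will be uninformative, flat priors". The reported summary is the posterior mean difference at 24 months with a 95% credible interval. No rule for declaring success is given.
- Section 13.4.1 justifies 226 participants by power described as the equivalent of 91% for a standardised effect of 0.525, and gives 80% for 150 participants.
- Section 13.4.1 also says: "Interim analyses can also be carried out at pre-specified points where decisions on the continuation of the trial can be taken". No such points appear there or in 13.7.

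**The concern.** Type 1 error is a property of a decision rule under repeated sampling. Calling the analysis Bayesian does not remove it. What matters is the prior, the threshold and how often the rule is applied. A flat prior does no shrinking, so the posterior gives an early, noisy estimate the same weight as a conventional analysis would.

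The sentence matters because it is the stated reason for allowing looks that nobody has calibrated and for leaving them out of the sample size. If a committee relied on it and stopped on an interim credible interval that excluded zero, the result would carry a higher false-positive risk than a reader of a 95% interval would assume, and that could not be put right afterwards. Nor can the protocol treat error rates as irrelevant to its framework: a power figure has no meaning without a success threshold, and a threshold brings a false-positive rate with it.

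**Working it through.** **Inputs.** From the protocol: N = 226 or 150, 1:1 allocation, SD 10, standardised effect 0.525 (5.25 points), flat priors, 95% credible interval. Assumed, because not stated: success means that the 95% interval excludes zero at any analysis, and analyses are equally spaced in information.

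**1. The stated power.** With Z-drift 0.525 / √(4/N):

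- N = 226: 0.525 × √56.5 = 3.946; Φ(3.946 − 1.960) = 97.7%, against 91% stated.
- N = 150: 0.525 × √37.5 = 3.215; Φ(3.215 − 1.960) = 89.5%, against 80% stated.

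Two-sided 5% with an assumed 25% loss gives 92.8% and 79.5%, each within 2 points of the stated figure. One-sided 5% with 40% loss gives 92.1% and 80.1%. Alpha, threshold and loss are not given, so the stated power can be neither confirmed nor called wrong. The later steps take 91% and 80% as given.

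**2. Flat prior and confidence interval.** Let the estimate be d, with variance v = 4 × 10² / N and prior SD τ. The posterior variance is 1/(1/v + 1/τ²), and the posterior mean is that variance times d/v. As τ goes to infinity, posterior mean over posterior SD becomes d/√v = Z. The interval then excludes zero exactly when |Z| > 1.96. This is exact for a normal likelihood with known variance and a close approximation for the planned mixed model.

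**3. False-positive rate under no effect.** This is P(|Z| > 1.96 at any of K analyses), from 2,000,000 simulated Z-paths. The check column uses 100,000 simulated two-arm trials of 226 participants (SD 10) with the flat-prior t posterior.

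| Analyses, including the final | Z-paths | Trials of 226 |
|---|---|---|
| 1 | 5.0% | 5.0% |
| 2 | 8.3% | 8.4% |
| 3 | 10.7% | 10.8% |
| 4 | 12.6% | 12.7% |
| 5 | 14.2% | 14.3% |

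Relative to 5%, one interim gives 8.3 / 5 = 1.7 times and four interims give 14.2 / 5 = 2.8 times.

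**4. Other success rules.** If success means a posterior probability of benefit above 0.975, the rate goes from 2.5% (one analysis) to 4.2% (two) and 7.1% (five). With a 0.95 cut-off it goes from 5.0% to 8.0% and 13.0%. The pattern is the same.

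**5. Dependence on the prior, two analyses.** Flat 8.3%; prior SD 10 points 7.9%; SD 5 points 6.7%; SD 2.5 points 3.6%. Any protection comes from the prior, and a flat one gives none.

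**6. Futility only.** Stopping when Z < 0 at half information leaves the upper-tail error at 2.46% against 2.5%, so there is no inflation. It costs about 0.2 points of power from 91%.

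**7. Power with looks.** The drift for 91% is 1.960 + 1.341 = 3.301, and for 80% it is 1.960 + 0.842 = 2.802. Results for two analyses:

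| Rule | Critical values | 91% design | 80% design |
|---|---|---|---|
| Uncorrected | 1.96, 1.96 | about 92% | about 82% |
| O'Brien-Fleming type | 2.797, 1.977 | 90.8% | 79.7% |
| Pocock type | 2.178, 2.178 | 88.2% | 75.6% |

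**The case against.** The best defence is that a posterior distribution is interpretable whatever the stopping rule, so a Bayesian need not adjust for looks. That is a coherent position on inference. The sentence in 13.7, however, is about type 1 error and sample size, and there the defence does not help, because a flat-prior rule has a long-run error rate and repeated efficacy looks raise it.

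Several limits on the point do stand:

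- No look is planned. Harm needs a called look, an efficacy purpose and an unadjusted threshold together. Section 13.4.1 raises interim analyses in the context of poor recruitment, and neither section names early declaration of efficacy as the aim, although stopping is not confined to futility or safety.
- The interval-excludes-zero rule is an assumption. Thresholds may sit in the SAP or a DMC document, neither of which is shown, so their absence from the protocol is not itself a fault.
- A reader might infer that looks would break the trial's stated operating characteristics. The protocol does not support that: it states power but no type 1 error rate for the trial, and uncorrected looks slightly raise power. What is broken is an implied 5%.
- A reader might also take the expected twice-yearly DMC meetings as efficacy looks. Section 14.3 has the DMC assess adverse event data, and 13.7 says no interim analysis happens unless it is called for.
- Sections 13.4.1 and 13.7 are not in flat contradiction, since 13.4.1 is permissive and points could be fixed if a look were called. The wording still needs aligning.

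**Conclusion.** The statement in 13.7 is wrong as written. With the flat priors of 13.5.1.1 and an unchanged 95% credible-interval rule, efficacy looks inflate the false-positive rate just as uncorrected frequentist looks do: about 8.3% with one interim, 10.7% with two and 14.2% with four, against an implied 5%. These figures rest on the assumed success rule and on equal spacing.

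It would go too far to say that the error rate is two to three times nominal in general. One interim gives 1.7 times, and doubling takes at least two interims plus the final analysis. Futility-only and safety looks add nothing, and the single final analysis now planned is sound on this point. This should be fixed, but the planned primary analysis does not depend on it.

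**What to change.** Delete from 13.7 the no-penalty sentence and the clause about sample size. Replace them with one of two rules:

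- Unscheduled looks are limited to safety and non-binding futility, with no efficacy claim.
- Any efficacy look has its number, timing and posterior-probability threshold fixed before data are seen, calibrated by simulation under the planned model and priors, with type 1 error and power both reported.

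Then align 13.4.1 with 13.7: either name the pre-specified points or say that none exists and that a look can arise only by committee recommendation under the rule above.

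The cost is protocol wording plus a simulation. With two analyses held to 5% overall, power from a 91% design falls by 0.2 points (O'Brien-Fleming type) or 2.8 points (Pocock type). From an 80% design, the fallback with 150 participants, it falls by 0.3 or 4.4 points. The safety-and-futility option needs no efficacy calibration, and the simple futility rule tested costs about 0.2 points of power.

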6.3 Blinding status of researchers

Individual blinding status	Blinded	Unblinded
Chief Investigators	X	
Principal Investigators and all other staff at site		X
Co-applicants	X	
Trial Managers		X

The electronic version of this document is the latest version. It is responsibility of the individual to ensure that any paper material is the current version. Printed material is uncontrolled documentation.

Senior Trial Statistician	X	
Trial Statistician		X
Pharmacists at site		X
Outcome Assessors/Research Nurses		X
Treating clinicians		X
Programme Steering Committee (TSC)	X	
Data Monitoring Committee (DMC)		X

Table 3 - blinding status of PATHWAYS researchers

The blinding status of the research team is detailed in Table 3 above. Trial statistician will be initially blinded to complete the Statistical Analysis Plan, then will be unblinded to complete DMC reports.

*For roles not listed please refer to study delegation logs.

7 Data Management

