14.1 Programme Management Group (PMG)

The PMG will be chaired by the PATHWAYS CI, [name], with membership comprising co-investigators and core members of the central research team.

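### Section 13.7 lets the DMC pass interim results to the PMG, which is chaired by a Chief Investigator listed as blinded and has no step in the decision chain

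*Protocol*

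**What the plan says.** Protocol section 13.7 opens with: "Currently, no interim analysis is planned either for futility or for efficacy in either TRIAL or HORIZON INTENSIVE". It then allows an interim if the DMC and PSC call for one, or the funder through the PSC. On access it says that "the results of any such analysis will be shared with the DMC only in the first instance", and continues: "It is then within the remit of the DMC to determine if it is important for the PSC or PMG should see the results". On decisions it says that "the PSC will advise the sponsor in making the final decision on stopping, continuation, or any potential extension to the funding period".

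Section 14.1 describes the body named in the access sentence: "The PMG will be chaired by the PATHWAYS CI", "with membership comprising co-investigators and core members of the central research team".

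Section 6.3 states: "The blinding status of the research team is detailed in Table 3 above". In that table the row "Chief Investigators" is marked blinded, as are the co-applicants, the Senior Trial Statistician and the PSC. Trial Managers, the Trial Statistician, site staff, outcome assessors, treating clinicians and the DMC are marked unblinded.

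**The concern.** The access sentence names the PMG beside the PSC, with no condition, purpose or safeguard attached. The PMG is the group that manages the trial day to day, and its chair is meant to be blinded.

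An open-label trial keeps its central investigators away from the emerging difference so that changes made during the trial can be shown not to depend on it. Participants cannot be blinded here (section 2.1.1) and site staff are not. What central blinding protects is therefore the independence of decisions about conduct. If the Chief Investigator sees the between-arm result while the length of recruitment or the timeline is still open, that independence can no longer be demonstrated for anything the Chief Investigator later proposes, however good the reasons.

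**Working it through.** The point rests on no figure in the protocol, so there is nothing to reproduce or recompute. The check is a comparison of the relevant sections.

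1. **Can interim results exist while the trial is open?** Yes. Section 13.7 plans none but allows one on request. Section 13.4.1 mentions interim analyses, alongside a longer recruitment period, where it discusses failure to reach 226 participants. Section 3.2.1 also foresees extending recruitment if rates are low. An interim could therefore coincide with an open question about how long to recruit.

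2. **Who may see the results?** Section 13.7: the DMC first, then the PSC or the PMG if the DMC judges it important.

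3. **Who sits on the PMG?** Section 14.1: the Chief Investigator as chair, with co-investigators and core central staff.

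4. **What is their listed status?** Table 3 marks Chief Investigators as blinded. It has no row for co-investigators; the nearest is co-applicants, also blinded. Trial Managers, who may be among the core central staff, are already unblinded. The firm link is therefore the Chief Investigator, and it is enough for the point.

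5. **Does Table 3 provide for a change of status?** Only for the Trial Statistician, who is blinded while completing the SAP and then unblinded for DMC reports. Nothing similar is given for the Chief Investigator or the PSC.

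6. **Does the PMG need the results?** In section 13.7 the DMC recommends to the PSC, and the PSC advises the sponsor, who decides. The PMG has no step. The section even foresees that the PSC may not need the data when the evidence is unambiguous.

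7. **What limits the damage?** Section 13.4.1 requires both the DMC and the PSC to approve amendments before they take effect, and says that eligibility cannot be widened or sites added. Section 3.2 bars the research team from trying to influence clinicians' views on eligibility. These restrict what could be changed, but they do not keep the person making a proposal blind.

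Putting 2, 3 and 4 together: using the permission for between-arm results would make the Chief Investigator's entry in Table 3 untrue. Step 6 shows that nothing in the stated process requires this.

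**The case against.** Several conditions must all hold before anything happens. An interim must be called, the DMC sees it first, and the DMC must then choose release. The one worked example in section 13.7 is restrictive, since it has the DMC withholding data even from the PSC. The DMC is independent and works to recognised guidance (section 14.3), and its charter, which is not shown, may restrict access further. All of this stands and is why the point is modest. It does not remove the point, because the protocol itself fixes who may receive results, and a charter barring the PMG would conflict with that text.

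A reader might also infer more than the documents support:

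- **That sections 13.7 and 6.3 flatly contradict each other.** They conflict only if the discretion is used. Table 3 gives a working status, and its note on the Trial Statistician shows that status can change.
- **That between-arm results will go to the PMG.** Section 13.7 speaks of results and limits the analysis to data the two committees consider relevant, which could be pooled or safety data. Between-arm is the natural reading in a section on futility, efficacy and stopping, but it is an inference.
- **That the whole PMG is a blinded group.** Step 4 shows otherwise.
- **That the PMG could steer the trial.** Amendments need DMC and PSC approval, and the sponsor decides on PSC advice. The Chief Investigator is among those who may stop the trial (sections 11 and 14.2), but on new safety information or reasons given by the bodies listed there.
- **That release would bias the self-reported KIDSCREEN-10.** Participants already know their arm, so the Chief Investigator's blinding does not protect measurement. Section 2.2 expects expectancy effects from allocation and preference; it does not describe leaked interim results.

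Finally, the PSC is also listed as blinded and is also a possible recipient. That is true, but the PSC has a decision to make. For the PSC a note in Table 3 is enough.

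**Conclusion.** The point holds in a limited form. Section 13.7 gives the DMC an unconditional option to share interim results with a group whose chair is listed as blinded and which has no part in the decision that an interim would inform. If between-arm results were released while recruitment or an extension was open, the listed blinding would be lost, and the Chief Investigator's later proposals could not be shown to be independent of the data.

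The size cannot be computed from the protocol. The consequence rests on three assumptions: that an interim is called although none is planned, that the DMC releases the results to the PMG, and that they are between-arm results. The approval rule for amendments mitigates part of the risk. This is a cheap improvement to governance wording; it does not put the primary analysis in doubt.

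**What to change.** - In section 13.7, delete the words 'or PMG' from the access sentence.
- State there that between-arm interim results go only to the DMC and, where a decision needs them, to the independent members of the PSC in closed session. The restriction to independent members matters because section 14.2 allows non-independent members on the PSC.
- State that the PMG and the Chief Investigator receive only the recommendation until database lock.
- Add a note to Table 3 that the PSC is blinded except for this conditional access.
- Use the same wording in the DMC and PSC charters.

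The cost is a few sentences in the protocol and matching charter text. Sample size, analysis and trial procedures do not change. The one small downside is that the PMG must act on a recommendation without seeing the data behind it.
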